2.2 Secondary objectives

To demonstrate that the proportion of patients experiencing intolerable drug-related adverse events is lower with a low than a standard dose.

To demonstrate that health-related quality of life (HRQOL) and satisfaction with treatment score higher with a low than a standard dose.

To demonstrate that, on a societal perspective, the treatment of newly diagnosed epilepsy with low AED doses will translate into savings in terms of contacts with the National Health System (in- and outpatient visits, drug expenditures).

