2.4 Secondary endpoints

Secondary endpoints include: 1. Treatment failure motivated by intolerable drug-related adverse events; 2. HRQOL total score at 12 months; 3. Patient's satisfaction at 12 months; 4. Total cost of health care resources consumed for the management of epilepsy during the first 12 months of the study.

3. Study design

This is a multicenter randomized pragmatic parallel-group single-blind non-inferiority trial. Italian epilepsy centers will participate in the study. Each center has been selected on the basis of high

standards in the management of epilepsy and on previous participation to studies coordinated by the PI.

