3.4 Randomization

After informed consent, eligible patients will be randomized to receive a low or a standard dose of the assigned drug. Randomization will be centralized at the Istituto Mario Negri IRCCS, Milano. Randomization sequence will be created using SAS 9.4 (SAS Institute, Cary, NC, USA) statistical software and will be stratified by center with a 1:1 allocation using random block sizes of 4. Each center will receive randomization scratch-cards.

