7.7 Scales and e-CRF

The QOLIE-31 inventory will be used at the baseline and last visit to measure HRQOL (Annex QOLIE-31). The Patient Satisfaction Questionnaire will be used at the baseline and last visit to measure patient's satisfaction (Annex PSQ-18).

The e-CRF used for the collection of demographic and clinical data is appended (Annex Case Report Form).

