10.4 Outcome measures, statistical methods and data analysis

Expected outcomes are the following:

1. compared to patients assigned to standard daily doses, patients receiving low daily doses of AEDs are expected to incur in similar rates of seizure recurrence;
2. compared to patients assigned to standard daily doses, patients receiving low daily doses of AEDs are expected to undergo significantly less treatment changes due to intolerable drug-related adverse events;
3. compared to patients assigned to standard daily doses, patients receiving low daily doses of AEDs are expected to experience less drug-related intolerable adverse events;
4. compared to patients assigned to standard daily doses, patients receiving low daily doses of AEDs are expected to experience a better quality of life;
5. the National Health System is expected to incur in significant savings with low daily doses of AEDs.

Primary outcome

The proportion of patients experiencing a treatment failure motivated by the need to change the assigned dose or the assigned drug for seizure relapse during the follow-up.

Secondary outcomes

1. the proportion of patients experiencing a treatment failure motivated by intolerable drug-related adverse events during the follow-up;
2. QOLIE-31 total score at the last visit;
3. the score of the seven PSQ-18 subscales (general satisfaction, technical quality, interpersonal manner, communication, financial aspects, time spent with doctor, accessibility and convenience) at the last visit;
4. the mean daily patient's cost of health care resources consumed for the management of epilepsy during the first 12 months of the study.

Descriptive statistics will be provided for all the data collected at admission, comparing the two

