treatment regimens. Numerical variables will be described using means, standard deviations, medians and ranges, while categorical variables using frequencies and percentages. The proportion of patients experiencing the primary end-point over the entire follow-up will be estimated using Kaplan-Meier survival curves. The difference between the two treatment arms in the proportion of patients experiencing the primary endpoint, with 95% confidence intervals (95% CI), will be calculated at 1, 3, 6, 9 and 12 months, and compared to the non-inferiority margin (m). In presence of variables at admission having a different distribution in the two treatment groups and that could have an effect on treatment response (possible confounders), a multivariable analysis will be also performed using a Cox's proportional hazards model, adjusted for these variables. A hazard ratio (HR), with the corresponding 95% CI, will be reported, and compared to a relative risk (RR) obtained considering as reference the proportion of patients experiencing the primary endpoint in the standard dose arm (p_0) and taking into account the non-inferiority margin ($RR=(p_0+m)/p_0$). The secondary end-point will be evaluated using Kaplan-Meier survival curves, comparing the two treatment arms with the log-rank test. In presence of possible confounders with a different distribution in the two treatment arms at baseline, a Cox's proportional hazards model will be used. The QOLIE-31 total score, the seven PSQ-18 subscales scores at the last visit, and mean daily patient's costs will be compared, separately, between treatment arms using the t-test, the Wilcoxon-Mann-Whitney test, or a multivariable linear regression model. Subgroup analyses will be performed separately for sex, age groups, drug, seizure types (focal/focal-to-bilateral), etiology (known/unknown), and center.

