| Neurological examination | X | | | | | X | X | X | X | X |
| Psychiatric examination | X | | | | | | | | | |
| Concomitant diseases | X | X | X | X | X | X | X | X | X | X |
| Concomitant treatments | X | X | X | X | X | X | X | X | X | X |
| Birth control | X | X | X | X | X | X | X | X | X | X |
| Epilepsy history | X | | | | | | | | | |

| | | | | | | | | | | |
|--|---|---|---|---|---|---|---|---|---|---|
| QOLIE 31 and PSQ-18 inventories | X | | | | | X | | | | |
| First interictal EEG | X | | | | | | | | | |
| Results of follow-up interictal EEG (if performed) | | X | X | X | X | X | X | X | X | X |
| Imaging (CT, MRI) findings | X | | | | | | | | | |
| AED plasma concentration and other biochemical/hematological parameters (if performed) | X | X | X | X | X | X | X | X | X | X |
| Randomization | X | | | | | | | | | |
| Assessment of seizures, AE/SAE | | X | X | X | X | X | X | X | X | X |
| Assessment of contacts with the NHS | | X | X | X | X | X | X | X | X | X |
| Delivery of patient's diary | X | | | | | | | | | |
| Assessment of patient's diary data | | X | X | X | X | X | X | X | X | X |
| Return of patient's diary | | | | | | X | | | | |
| Assessment of compliance | | X | X | X | X | X | X | X | X | X |

| | | | | | | | | | | |
|-----------------------------|---|---|---|---|---|---|---|---|---|---|
| Next contact/visit schedule | X | X | X | X | X | | X | X | X | X |
| Final questions | | | | | | X | | | | |

*Visit at 4 weeks, 3, 6 and 9 months will be performed by phone (TC). The other visits will be performed as clinic on-site visits.

PROTOCOL APPROVAL PAGE Version 3.0 December, 20 2021

[name]**Date**

Istituto di Ricerche Farmacologiche Mario Negri IRCCS
Milano, Italy

I have read the Protocol Final Version 3.0 Dec, 20 2021. I agree to conduct this study as outlined herein.

Investigator Name

Investigator Institution

Investigator Signature**Date**

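### The objective is satisfaction with treatment, but the measure is seven undesignated PSQ-18 subscales, five of which by name concern the doctor or the service

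*Combined protocol and SAP*

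**What the plan says.** Section 2.2 sets out to demonstrate that HRQOL and "satisfaction with treatment score higher with a low than a standard dose". Section 2.4 makes this a single secondary endpoint, "Patient's satisfaction at 12 months", and names no score. Section 7.7 names the instrument: "The Patient Satisfaction Questionnaire will be used at the baseline and last visit to measure patient's satisfaction". It refers to an annex for the questionnaire itself.

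Section 10.4 gives, as the third of four secondary outcomes, "the score of the seven PSQ-18 subscales (general satisfaction, technical quality, interpersonal manner, communication, financial aspects, time spent with doctor, accessibility and convenience", all taken at the last visit. Its analysis paragraph states that "the seven PSQ-18 subscales scores at the last visit, and mean daily patient's costs will be compared, separately, between treatment arms", and that this is done "using the t-test, the Wilcoxon-Mann-Whitney test, or a multivariable linear regression model".

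For PSQ-18 the plan names no key subscale, total score, testing order or multiplicity adjustment, and no rule for choosing among the three methods. HRQOL is handled differently in the same section: one QOLIE-31 total score is the outcome.

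**The concern.** There are two linked problems. The objective concerns satisfaction with the assigned treatment, while most of the listed subscales, by their names, rate the doctor and the service. In addition, one endpoint in 2.4 becomes seven separate comparisons in 10.4, with nothing to say which of them decides whether the objective is met.

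If the plan is followed as written, a null result would say little about satisfaction with the dose. A single significant subscale, such as time spent with the doctor, could be reported as meeting the objective in 2.2. Neither conclusion would be sound.

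**Working it through.** **1. The plan's own figure.** The plan gives no error rate or power for satisfaction. Its only related figure is the sample size in 10.6, which reproduces with 60% in both arms, a margin of 0.15, one-sided 0.025 and 80% power:

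- n = (1.960 + 0.842)² × (2 × 0.6 × 0.4) / 0.15² = 7.849 × 0.48 / 0.0225 = 167.4, so 168 per arm.
- With 10% dropout: 168 / 0.90 = 186.7, so 187 per arm and 374 in total.

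**2. Subscale names against the objective.** The PSQ-18 annex was not available, so this rests on the names in 10.4.

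- Doctor or service by name (five): technical quality, interpersonal manner, communication, time spent with doctor, accessibility and convenience.
- Not limited by name to the doctor or service (two): general satisfaction and financial aspects. Financial aspects is a weak route to a dose effect, since 6.7 has drug costs covered by the national health service.
- Naming the drug or the dose: none.

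Timing points the same way. PSQ-18 is also given at baseline (7.1), to patients whom 3.2 requires to be newly diagnosed and not yet treated. Most have no antiepileptic treatment to rate at that visit.

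**3. Chance of a false-positive subscale.** Assumption: each subscale is tested at 0.05 two-sided, because the documents give no alpha for secondary outcomes. With no true effect and independent subscales:

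- at least one significant in either direction: 1 − 0.95⁷ = 0.302
- at least one significant in favour of low dose: 1 − 0.975⁷ = 0.162

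Subscales of one questionnaire are likely to be correlated. The documents give no correlation, so a range is shown. The correlated rows come from simulating seven equally correlated normal statistics (400,000 draws).

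| Common correlation | Either direction | In favour of low dose |
|---|---|---|
| 0 | 30% | 16% |
| 0.3 | 27% | 14% |
| 0.5 | 23% | 12% |
| 0.7 | 18% | 9% |
| 0.9 | 11% | 6% |
| One score named in advance | 5% | 2.5% |

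The objective is directional, so the right-hand column is the more relevant one.

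**4. Naming one score compared with adjusting all seven.** With 168 evaluable patients per arm and 80% power, the detectable difference in SD units is (z for alpha + 0.842) × √(2/168), where √(2/168) = 0.109.

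- One named score at 0.05: (1.960 + 0.842) × 0.109 = 0.31 SD.
- Bonferroni at 0.05 / 7 = 0.0071 per subscale: 0.39 SD, with family-wise error 1 − (1 − 0.0071)⁷ = 4.9% if independent.

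Naming one score therefore controls the error without the loss of sensitivity that adjusting all seven would bring.

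**5. Attribution.** Section 6.4 limits blinding to the evaluating physician, so patients and treating physicians know the dose. Sections 3.6 and 7.2 leave the timing of interim on-site visits to the caring physician. A difference in, say, time spent with the doctor could reflect visit frequency or expectation rather than satisfaction with the dose.

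**The case against.** The strongest reply is that satisfaction is a supportive outcome. It is third of four secondary outcomes, is absent from the five expected outcomes in 10.4, and affects neither the primary non-inferiority comparison nor the sample size. Reporting every subscale of a questionnaire without adjustment is common. The 30% figure is an upper bound: it needs independence, an assumed alpha, and counting of differences in either direction. All of this stands, and it limits the weight of the point. It does not remove it, because 2.2 says the trial will demonstrate the effect and the plan does not say which result would do so.

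A reader might infer that a dose effect on satisfaction cannot be shown at all. The documents do not support that. General satisfaction could respond to tolerability, and 2.2 itself expects fewer health-service contacts and lower drug spending on low dose, so ratings of time, access or cost could change as a consequence of dose.

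A reader might also infer that care is identical in both arms because randomization "will be stratified by center with a 1:1 allocation". Stratification balances who enters each arm at a center. It does not equalise the care given afterwards by unblinded physicians with discretionary visits.

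It would likewise be too strong to say that six or more of the seven subscales concern only the physician and the service. By name it is five, and the items themselves could not be checked.

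**Conclusion.** The point holds as one of mismatch and missing pre-specification. PSQ-18, as listed, is poorly matched to an objective on satisfaction with treatment and is probably insensitive to dose. Any difference it shows would be hard to attribute to satisfaction with the dose. Seven separate comparisons with none designated carry roughly an 11% to 30% chance of at least one false-positive subscale, and 6% to 16% in favour of low dose, against 2.5% for one named score. These figures rest on 5% two-sided testing per subscale, no true effect, and a common correlation between 0 and 0.9. The reading of the content rests on subscale names alone. The consequence is confined to one secondary objective, but it changes what the trial may claim about it.

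**What to change.** In 2.2, 2.4 and 10.4:

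- Restate the objective as patient satisfaction with care as measured by PSQ-18.
- Name the general satisfaction subscale at 12 months as the single satisfaction endpoint, and use the same time point throughout (2.4 says 12 months, 10.4 the last visit).
- State one analysis method for that score and how its baseline value is used. The 2.5% figure presumes one pre-specified test.
- Report the other six subscales descriptively.

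This needs only wording, with no extra patients, visits or questionnaires. The cost is that the other six subscales get no formal test and the claim is narrower.

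If the sponsor wants to keep an objective on satisfaction with treatment, it should first check whether the flow-chart row "Final questions" at the end-of-study visit already contains such an item; the documents do not describe that row. A newly added single item would be a weaker choice: it would have no baseline value and limited validation, and it would be open to expectation bias in patients who know their dose.

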6.5 Brand & generic drugs

For each product, the treating physician can use the brand or the generic formulation. However, physicians and patients will be allowed to shift from brand to a generic formulation (where available) and vice versa and from one generic formulation to another during the study period.

6.6 Need to change the study drug or add another compound and premature withdrawal

An unscheduled phone contact will also take place soon after a relapse: the patients will also be instructed to call a member of the study staff within 24 h after an ictal event. If the study staff is confident about the epileptic nature of the event, the treating physician may decide to modify the treatment schedule; the patient will be thus instructed to change the AED doses or the treatment and come for the final visit within 72 hours. Otherwise, the patient will be invited to come for a clinic visit within the next 72 hours.

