Follow-up visits will be scheduled at the discretion of the caring physician but telephone contacts will be programmed at 4 weeks, 3, 6, 9 and an on-site clinic visit at 12 months. An interval of ± 1 week for the visit schedule is permitted. During each contact the patient will be asked to report any seizure recurrence, adverse event and any additional information deemed important for the management of the disease. Patients will be invited to read the diaries and verify if any missing or incomplete information was present.

The following evaluations will be performed during site visits:

1. Evaluation of possible relapses, compliance with treatment schedule and adverse events;
2. Recording of clinical parameters: weight, arterial blood pressure, heart rate;
3. Neurological examination;
4. General clinical history: concomitant diseases and medications;
5. Recording of the plasma concentration of the assigned drug and laboratory examinations previously specified (only if required as per clinical practice);
6. Administration of the QOLIE-31 and PSQ-18 inventories (only at 12 months);
7. Report of a standard, interictal EEG if performed as per clinical practice;
8. Report of the daily intake of assigned drug and timing of the assigned dose;
9. Report of all the contacts with the National Health System (NHS) for the management of seizures and AEDs;
10. Receipt of the seizure diary, control for quality and completeness, and delivery of a new diary.

The diaries will be examined by an investigator different from the treating physician (the evaluating physician) who will be blinded to the assigned drug schedule

The following evaluations will be performed during phone contacts:

1. Evaluation of possible relapses, compliance with treatment schedule and adverse events;
2. General clinical history: concomitant diseases and medications;
3. Report of the daily intake and timing of the assigned dose;
4. Report of a standard, interictal EEG, if performed;
5. Recording of the plasma concentration of the assigned drug and laboratory examinations previously specified, if performed;
6. Report of all the contacts with the NHS for the management of seizures and AEDs.

In case of seizure relapse or treatment change due to adverse events, the patient will exit the study and antiepileptic treatment will be modified if required by the treating physician.

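### The cost endpoint is total 12-month cost in 2.4 but mean daily cost in 10.4, and no cost data are planned after exit at failure, so the savings comparison is biased if failure rates differ between arms

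*Combined protocol and SAP*

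**What the plan says.** Section 2.4 lists as its fourth secondary endpoint "Total cost of health care resources consumed for the management of epilepsy during the first 12 months of the study". Section 10.4 lists instead "the mean daily patient's cost of health care resources consumed for the management of epilepsy during the first 12 months of the study". The analysis paragraph of 10.4 covers only the second: "mean daily patient's costs will be compared, separately, between treatment arms using the t-test, the Wilcoxon-Mann-Whitney test, or a multivariable linear regression model". That list of methods also serves the QOLIE-31 and PSQ-18 scores, with no rule for choosing among them. The divisor of the daily cost is not defined, and no method is given for patients with incomplete cost follow-up.

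On observation time, 7.2 states: "In case of seizure relapse or treatment change due to adverse events, the patient will exit the study". Under 6.6, a patient whose treatment is changed after a relapse is told to "come for the final visit within 72 hours"; 7.4 sets the same interval for seizures or non-compliance. Contacts with the National Health System are noted in the patient diary (3.5), and the diary is handed in at the final visit (7.3). The flow-chart places the assessment of these contacts at the 4-week, 3-, 6- and 9-month calls, at discretionary site visits and at the end-of-study visit, and nowhere later. Sections 3.5 and 7 nevertheless say that patients are followed for 12 months.

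Section 2.2 sets the savings objective "on a societal perspective", but the same sentence counts savings as National Health System visits and drug spending.

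**The concern.** The two definitions are different endpoints unless everyone is observed for the full year, and the exit rule means that many patients will not be. A total cut off at exit makes an early failure look cheap, because spending is no longer recorded. A daily average taken per patient can make the same failure look dear, because the relapse contact is divided by few days.

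The unrecorded part is not a random sample of time. It is the period after failure, when a new regimen, extra visits and admissions would fall. The objective is to show that low dose saves money, and the design tolerates somewhat more relapses on low dose. A savings result could therefore depend on which section's definition the analyst follows.

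There are two smaller points. The Wilcoxon-Mann-Whitney test does not compare arithmetic means, which are what determine a payer's saving. And the stated perspective is wider than the costs that 2.2 itself names.

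**Working it through.** **Inputs from the plan (10.6).** 60% seizure-free in both arms, hence 40% relapse; margin up to 15 points absolute; one-sided 0.025; 80% power; 168 per arm; 374 in total. These reproduce: 2 × 0.6 × 0.4 × (1.960 + 0.842)² / 0.15² = 167.4, so 168; 336/0.9 = 373.3, so 374. The plan gives no cost mean, SD or target difference, so every cost value below is an assumption for illustration.

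**1. When the definitions agree.** With cost C and observed days T, total = C and daily = C/T. They are proportional only if T = 365 for all. Example: one patient costs 1 unit a day for the year (total 365, daily 1.00). Another exits on day 90 having cost 100 (total 100, daily 100/90 = 1.11). The second is cheaper on the total and dearer per day.

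**2. Person-time without cost data.** Assume a constant hazard, exit at every relapse, and adverse-event exits as shown (the plan gives no rate). With S the proportion not exited at month 12, the observed share is (1 − S)/(−ln S).

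| Adverse-event exits | S | Exits among 336 | Observed share | Lost |
|---|---|---|---|---|
| 0 | 0.60 | 134 | 0.40/0.511 = 0.783 | 22% |
| 10% | 0.54 | 155 | 0.46/0.616 = 0.747 | 25% |
| 20% | 0.48 | 175 | 0.52/0.734 = 0.708 | 29% |

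**3. Effect on the arm comparison.** Assume relapse exits only; cost before exit 0.8 a day (low) and 1.0 a day (standard); acute cost A recorded at exit; cost k a day from failure to month 12, unrecorded. With relapse p and L = −ln(1 − p), the observed share is m = p/L. Then:

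- observed total = 365·c·m + A·p, where c is the daily cost before exit
- full 12-month total = observed total + 365·k·(1 − m)
- pooled daily cost (arm cost over arm days) = c + A·L/365

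The mean of per-patient daily costs was simulated (400,000 patients per arm, minimum one day). Standard-arm relapse is 40% (m = 0.783). For low dose, m = 0.783, 0.721 and 0.689 at 40%, 50% and 55%. Entries are low minus standard.

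| Low relapse | A | k | Observed total | Per-patient daily | Pooled daily | Full total |
|---|---|---|---|---|---|---|
| 40% | 0 | 3 | −57 | −0.20 | −0.20 | −57 |
| 50% | 0 | 3 | −75 | −0.20 | −0.20 | −8 |
| 50% | 300 | 3 | −45 | about +0.6 | −0.05 | +22 |
| 55% | 0 | 1 | −85 | −0.20 | −0.20 | −50 |
| 55% | 0 | 3 | −85 | −0.20 | −0.20 | +18.5 |
| 55% | 300 | 1 | −40 | about +1.0 | +0.04 | −5 |
| 55% | 300 | 3 | −40 | about +1.1 | +0.04 | +63.5 |

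Example, 55% with A = 0 and k = 3. Observed: 0.8 × 365 × 0.6888 = 201.1 against 365 × 0.7830 = 285.8, difference −84.7. Unrecorded: 1095 × 0.3112 = 340.8 against 1095 × 0.2170 = 237.6. Full: 541.9 − 523.4 = +18.5. Adding A = 300 adds 300 × 0.15 = 45 to both differences.

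The per-patient daily figure does not depend on k, so about +1.0 and +1.1 are the same quantity with simulation noise.

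**Reading.** At equal relapse the sign is the same on every measure. With more relapses on low dose, the observed total overstates the saving in every row. The per-patient daily cost agrees with it in sign when A = 0 and has the opposite sign when A = 300.

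**The case against.** The best reply is that the plan captures more than it first appears to. Dated contacts go into the diary and are reviewed at every call and at the final visit, so the immediate cost of a relapse, up to about 72 hours, can be recorded. This stands. A reader might infer that the cost of treatment failure is left out altogether; the documents do not support that. What has no planned collection is the later cost, to month 12.

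Nor does any passage say that cost recording stops at exit. That is an inference from the exit rule, the diary return and the flow-chart, and it conflicts with the 12-month follow-up in 3.5 and 7. The conflict is itself part of the point, because no procedure delivers that follow-up after exit.

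A reader might also infer that low dose must look cheaper than it is. That does not follow. 10.4 analyses daily cost, which can penalise early failures, and adverse-event exits, which 10.4 expects more often on standard dose, remove later costs from that arm too. At the planning assumption of equal relapse, the illustration keeps its sign.

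A striking multiple is available as well: a contact in a patient who exits on day 10 weighs 365/10 = 36.5 times one in a patient followed all year. It needs a per-patient divisor, which the plan does not specify, and only about 1.7–2.0% would exit by day 10 under the hazards above (1 − exp(−L × 10/365), L = 0.616 to 0.734).

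Finally, the t-test and regression are already among the permitted methods, and the perspective is a matter of labelling. Both are minor. Whether other costs are collected cannot be checked, since the case report form and diary annexes are not among the documents.

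**Conclusion.** The conflict between 2.4 and 10.4 is wrong as written and needs no assumption to establish. The absence of planned cost collection after exit is a sound inference from several sections that contradict the stated 12-month follow-up.

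The lost share, about 22% of person-time from relapse alone and 25–29% with adverse-event exits, rests on a constant hazard, exit at every relapse and assumed adverse-event rates. It also ignores dropout and exits for poor compliance. It measures missing data, not bias between arms.

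Bias arises if failure rates differ. Truncated totals understate the arm with more failures, and per-patient daily averages can overstate it. Reversal of the full-cost sign appears only under some assumed costs and relapse differences of 10 to 15 points, the latter being the edge of the margin. The net direction is not known in advance. The plan should be corrected, but the primary endpoint and sample size are unaffected.

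**What to change.** 1. State one endpoint in 2.4 and 10.4: total National Health System cost from randomization to month 12 in all randomized patients.
2. Reconcile the exit and diary-return passages (6.6, 7.2, 7.3, 7.4) with the 12-month follow-up in 3.5 and 7, so that leaving the assigned treatment does not end cost recording. This concerns data collection only.
3. Record National Health System contacts after exit at the 4-week, 3-, 6- and 9-month calls plus one month-12 contact, which may be by phone. The scheduled calls alone stop at month 9.
4. If step 3 is not done, prespecify a censored-cost method such as inverse-probability-weighted mean cost and state its assumption about exit. This is second best: it takes exited patients to have the later costs of comparable patients still observed, which is hard to defend when exit is the failure itself.
5. Compare arithmetic mean cost by t-test or regression with a bootstrap 95% CI, and drop the Wilcoxon-Mann-Whitney test for cost.
6. Call the perspective National Health System in 2.2.

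The cost is wording in several sections and up to five short remote contacts per exited patient. No change to sample size is needed.

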10.6 Sample size calculation

The sample size is based on the primary efficacy end-point. The non-inferiority margin is a relative 20% difference, as stipulated by the ILAE, up to a maximum of an absolute 15% difference between the two dosing schedules for the primary endpoint. Assuming a one-sided p of 0.025 and that the proportion of patients who will not have a seizure in the low dose and standard dose groups is 60%, 168 patients per group provides 80% power to test whether a low AED dose is non-inferior

to a standard dose. Assuming 10% drop-out rate, the required sample size will be 374 patients.

11 Administrative procedures

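### The non-inferiority margin is defined as 20% relative, but the analysis compares an absolute difference with an m that has no stated value, base or sampling error; no reading gives the stated margin, error and power together

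*Combined protocol and SAP*

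**What the plan says.** Section 10.6 gives the margin: "The non-inferiority margin is a relative 20% difference, as stipulated by the ILAE, up to a maximum of an absolute 15% difference". It also gives the design inputs: "Assuming a one-sided p of 0.025", and "the proportion of patients who will not have a seizure in the low dose and standard dose groups is 60" per cent. From these it states that "168 patients per group provides 80% power to test whether a low AED dose is non-inferior", and then "Assuming 10% drop-out rate, the required sample size will be 374 patients".

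Section 10.4 estimates the proportions by Kaplan-Meier. At 1, 3, 6, 9 and 12 months it takes the difference between arms with a 95% interval, "and compared to the non-inferiority margin (m"). If baseline imbalances call for it, a Cox model is added. Its hazard ratio is judged against (p_0 + m)/p_0, "considering as reference the proportion of patients experiencing the primary endpoint in the standard dose arm".

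Neither section gives m a number, says whether it is fixed in advance or computed from the data, or says which proportion the 20% is taken of. The scale differs across the document. Section 2.1 and the sample size speak of remaining seizure-free. Section 2.3, the primary outcome in 10.4 and p_0 are treatment failures for relapse.

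**The concern.** A relative margin with an absolute cap is a function of the standard-arm rate. Comparing an interval for a plain difference with m is a correct 2.5% test only if m is a constant. If m is computed from the observed standard-arm rate, it is random and correlated with the estimated difference, so the interval's standard error is the wrong one for the decision. If m is frozen at one number, the test no longer follows the relative definition except at particular standard-arm rates.

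This is the trial's only confirmatory decision. While m is unspecified, different analysts could reach different conclusions from the same data, and m could be settled after results are known.

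**Working it through.** **Inputs.** From 10.6: one-sided 0.025, 80% power, 60% seizure-free in both arms, 20% relative margin with a 15-point cap, 168 per arm, 10% drop-out. From 3.4: 1:1 allocation. Assumptions made here: failure is the complement of seizure-free (40%), follow-up is complete, and intervals are Wald intervals. S and F are the seizure-free and failure proportions, V is a variance, and n = 168.

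**1. The plan's own figure.** n = (1.960 + 0.842)² × (0.24 + 0.24)/m².
- m = 0.15: 168 per arm, and 336/0.9 gives 374. This reproduces the plan.
- m = 0.12 (20% of 60%): 262 per arm.
- m = 0.08 (20% of 40%): 589 per arm.

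So the sample size rests on a constant 15 points. Power with 168 per arm, Φ(m/√(0.48/168) − 1.96), is 80.1%, 61.2% and 32.2% for m = 0.15, 0.12 and 0.08.

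**2. m = 20% of the observed seizure-free rate.** The decision quantity is S_low − 0.8·S_std, with variance V_low + 0.64·V_std. The planned interval uses V_low + V_std.
- At the boundary, 60% v 48%: SE used = √((0.2496 + 0.24)/168) = 0.0540. Correct SE = √((0.2496 + 0.1536)/168) = 0.0490.
- Error = P(Z > 1.96 × 0.0540/0.0490) = 1.54% (simulated 1.52%, 2,000,000 trials).
- Power at 60% in both arms: SE used 0.05345, correct SE 0.04840. Φ((0.12 − 1.96 × 0.05345)/0.04840) = 62.4% (simulated 62.7%).
- The direct test has Φ(0.12/0.04840 − 1.96) = 69.8%.

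**3. m = 20% of the observed failure rate.** The decision quantity is F_low − 1.2·F_std, with variance V_low + 1.44·V_std.
- At 40% v 48% failure: SE used 0.0540, correct SE = √((0.2496 + 0.3456)/168) = 0.0595.
- Error = P(Z > 1.96 × 0.0540/0.0595) = 3.77% (simulated 3.84%).
- Power at 40% in both arms is 33.7%, against 27.3% for the direct test.

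**4. m fixed.**
- m = 0.15 at its own boundary, 60% v 45%: simulated error 2.55%.
- m = 0.15 at 60% v 48% (20% worse in relative terms): P(Z > 1.96 − 0.03/0.0540) = 8.0% (simulated 8.1%).
- m = 0.12: 5.7% at 50% v 40% and 0.9% at 70% v 56%.
- On the seizure-free scale, 12 points equals the stated margin only at a standard-arm rate of 60%. Fifteen points equals it at 75% (0.15/0.20) and, through the cap, above that.

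**5. Cox limit.** At p_0 = 0.40, (p_0 + m)/p_0 is 1.20, 1.30 or 1.375 for m = 0.08, 0.12 or 0.15.

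**6. Direct test.** The seizure-free contrast combined with the 15-point cap has simulated error 2.48% and power 69.8%. Eighty per cent power for the contrast would need 215 per arm on the seizure-free scale or 719 on the failure scale.

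**The case against.** The strongest reply is that m is simply 15 points. It is the only candidate value that reproduces 168, and comparing a 95% interval with a number fixed in advance is the standard test, with 2.5% error against its own null. Fixing an absolute margin at the planning stage is common practice. All of that stands. A reader might infer that the plan computes m from the data and therefore has the wrong error rate; the documents do not say so. A reader might also take the 8% as a type I error of the 15-point test. It is not: it measures how far that test departs from the relative definition.

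The reply does not close the matter. Section 10.6 calls 15 points the maximum, and at its own planning rate the relative rule gives 12 points, or 8 on failures. A constant 15 is therefore not the margin as written. The ILAE source may say whether the 20% attaches to a planning rate or an observed rate, but the protocol does not.

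A further tempting inference is that the rule always gives away power. It does so only on the seizure-free scale. On the failure scale, on which the endpoint and p_0 are defined, the direction reverses: the error is above 2.5%, and power exceeds that of the direct test.

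The Cox comparison is conditional and additional, so it is a secondary place where the same gap appears.

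**Conclusion.** The point holds as a gap in the decision rule, not as proof of a wrong error rate. On no reading does the plan deliver the stated relative margin, one-sided 2.5% error and 80% power at once. An observed m gives an error of 1.5% or 3.8% depending on its base. A fixed 15 points keeps 2.5% and 80%, but for a looser margin than the one defined at the planned rate.

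The figures rest on 168 evaluable patients per arm, binomial proportions and failure as the complement of seizure-free. Censoring would change the Kaplan-Meier standard errors but not the direction of the effects. The rates in step 2 move little with the standard-arm rate (1.50% to 1.63% for 50% to 75% seizure-free), as do those in step 3 (3.72% to 3.83% for 25% to 50% failure). It should be settled before any comparative data are seen.

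**What to change.** In 10.4, state the base of the 20% and choose one of two routes.

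**Keep the relative margin.** At 12 months, conclude non-inferiority only if both conditions hold:
- (i) the lower limit of the two-sided 95% CI for S_low − 0.8·S_std is above 0, with Greenwood variances combined as V_low + 0.64·V_std. On the failure scale, the upper limit for F_low − 1.2·F_std must be below 0, with V_low + 1.44·V_std;
- (ii) the lower limit for S_low − S_std is above −0.15.

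Both must hold, so no alpha adjustment is needed. In 10.6, replace 80% with the power of the chosen rule: about 70% on the seizure-free scale or about 27% on the failure scale.

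**Adopt a fixed absolute margin.** State the number in 10.4 and 10.6, remove the relative definition, and quote the matching power: 80% at 15 points, 61% at 12, 32% at 8.

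On either route, the Cox limit should use the same base and say where p_0 comes from.

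The cost is a paragraph in 10.4 and a revised power statement in 10.6, with no new data. The downside is that the stated power becomes less favourable unless the fixed 15-point margin is openly adopted; restoring 80% for the relative margin would need the larger samples in step 6.
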